### **Data Management and Analysis**

Data Management will be conducted with the support of the Data management unit in the Department of Epidemiology of NMIMR. A database will be created to manage the data. Data will be entered into Epi-info and analysed using SPSS. The unit of enrolment will be the household. Malaria prevalence will be reported as, proportion of subjects identified during the study period with RDT confirmed clinical malaria with

temperature  $\geq 37.5$  or asymptomatic parasitaemia and stratified by subject characteristics, including age, sex and community. A Chi square statistic will be used to compare prevalence across age and gender categories as well as communities.

**To determine whether interventions had an effect on the prevalence of malaria in the area, the baseline prevalence data will be compared with the evaluation data. Also a cost benefit analysis will be conducted by comparing what the NMCP put in in previous years to treat malaria to what it would spend if MTTT is implemented.**

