### **Study Design:**

This is an Implementation Research (IR) with a longitudinal cohort design to be undertaken within a two year frame work. The interventions are designed to compare the baseline to evaluation findings following the modified protocol of (Ahorlu et al., 2011). **There are two components to this implementation study a). The longitudinal (cohort) study: This is basically the prevalence surveys to be conducted with the selected cohort of children 6 months to 15 years – at baseline and before each of the subsequent MTTT rounds. b). The Survey involves using structured questionnaire to interview caretakers of children under five to solicit their views on the implementation process perceived benefits and challenges etc.** Though the target group is children from 6 months to 15 years of age, all parasitised adults will be cleared of the parasite during the interventions as well to reduce the parasite reservoirs. **Prevalence of malaria**

**trends in cohort group over the study period will reveal the effect of MTTT scale-up on the children 6month to 15 years.** Between interventions, the teams will conduct homes-based management of malaria for all febrile cases confirmed to be positive for malaria parasites. The challenges faced by the implementation team will be documented at every stage and discussed with all the stakeholders at every stage of the implementation.

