## **Methodology**

### **Study Area**

Pakro is one of five sub-districts in the Akwapim south district health directorate (DHD) in the Eastern region of Ghana (DHD, 2014). The Akwapim south district lies within the semi-equatorial climatic region, and experiences two rainfall seasons in a year, with an average rainfall of 125cm to 200cm. The first rainy season begins from May to June with the heaviest rainfall in June, whilst the second rainy season begins from September to October. According to the Ghana Statistical Service (GSS), the average household size in the Akwapim South district is estimated to be 4.0 whilst the average number of households per house or compound is estimated to be 1.6 (GSS, 2010). The Pakro sub-district has an estimated population of 7,889, and is bounded to the east by Akwapim North district; to the north by Ayensuano district; and to the west by Nsawam Adoagyiri Municipality. The sub-district is made up of 22 communities, and has 3 health care facilities (1 Health Centre and 2 Community-Based Health Planning Service (CHPS) compounds) (DHD, 2014). Due to limited resources, only seven communities will be selected for this study. This include Abeasi Newsite, Fante Town, Zongo (Adjenase/Kweitey), Piem/odumsisi, Adesa Latebibio, Sacchi/Tabankro and Odum Tokuro. These are communities with a relatively high population density. The Pakro Health Centre is one of thirty sentinel sites monitoring malaria prevalence in the country coordinated by the Noguchi Memorial Institute for Medical Research (NMIMR). Malaria parasite positivity rate was estimated to be 45.7% in 2014 (DHD, 2014). In the same year anaemia among pregnant women at 36 weeks of gestation was 21% (DHD, 2014).

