### **Study participants**

Community entry activities to sensitise the chiefs and the general population will be conducted at the beginning of the study through meetings and durbars (Ansah et al., 2015; Ahorlu, et al., 2009). Once the community leaders and the population have accepted the project, the household will be numbered and participants per household will be registered during a household census. All households will be given a unique identification code. Each individual within the household will be assigned a code that links them to a particular household and community. After obtaining consent from the household heads, the children will be enrolled but individual assent and consent will be obtained from the other adolescents and adults in the household. **A cohort of 460 children age 6 months to 15 years will be selected and enrolled into the longitudinal study which will consist of prevalence surveys undertaken before each MTTT. Caregivers of the children in the cohort will be enrolled for the community surveys using questionnaires. In this implementation research the entire population of the seven selected communities will be tested, treated and tracked. This is intended to clear the parasite pool in the community.**

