## Explanation of Budget

### Intervention team members

The project team will be composed of one Principal Investigator (PI), 1 research assistant, and 14 community workers and a driver. We will require two cars for each survey which will last 16 days. Surveys will take place quarterly, making a total of 6 interventions over two years.

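### The chi-square specified for comparing communities ignores household clustering, and the survey it applies to is not named

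*Protocol*

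**What the plan says.** Under Data Management and Analysis the protocol says "A Chi square statistic will be used to compare prevalence across age and gender categories as well as communities". It is the only significance test named in the document. The same section says "The unit of enrolment will be the household" and defines malaria prevalence as the "proportion of subjects identified during the study period with RDT confirmed clinical malaria with" fever, or with asymptomatic parasitaemia. It does not say whether the chi-square uses the cohort or all residents, or which survey supplies the data.

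On the structure of the data:

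- Study Area: "the average household size in the Akwapim South district is estimated to be 4.0".
- Study participants and Intermittent preventive treatment for the household members: all residents of the seven communities from 6 months of age are tested house to house.
- Study participants: "A cohort of 460 children age 6 months to 15 years will be selected and enrolled into the longitudinal study". Study Design has these children surveyed "at baseline and before each of the subsequent MTTT rounds".
- Work Plan and Intervention team members: six surveys, "making a total of 6 interventions over two years".

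On change over time, Data Management and Analysis says only that "the baseline prevalence data will be compared with the evaluation data". No test is named for that comparison.

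**The concern.** A Pearson chi-square takes its reference distribution from independent subjects. People in one household share exposure, so their infection status is likely to be correlated. Community is constant within a household, so correlated members carry less information about a community than their number suggests. The ordinary test does not allow for this and rejects too often. The stake is that prevalence differences between communities could be reported as real when they reflect household clustering.

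A second exposure is conditional. The same children are tested at up to six surveys, and the plan does not tie the test to one of them. If the six results per child were entered as separate records, repeated results on a child would be counted as if they came from different children. Contrasts by age and sex would then be affected as well as contrasts by community.

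**Working it through.** **The plan's own figure.** Sample size uses the Yamane formula: 4500 / (1 + 4500 × 0.05²) = 367.3, rounded up to 368, and 368 / (1 − 0.2) = 460. Both figures reproduce (the printed numerator of 38 has to be read as 368). The formula contains no allowance for clustering. The protocol states no error rate or within-household correlation, so the correlations below are assumptions shown as ranges.

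**1. Communities compared on all residents at one survey.** Inputs: household size m = 4.0 (Study Area); seven communities, hence 6 df; assumed within-household correlation (ICC) 0.1 to 0.3. Design effect DE = 1 + (m − 1) × ICC. True size = P(χ² on 6 df > 12.592 / DE), where 12.592 is the 5% critical value.

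| ICC | DE | 12.592 / DE | True size |
|---|---|---|---|
| 0.1 | 1.3 | 9.69 | 13.9% |
| 0.2 | 1.6 | 7.87 | 24.8% |
| 0.3 | 1.9 | 6.63 | 35.7% |

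A comparison of just two communities (1 df, critical value 3.841) gives 8.6%, 12.1% and 15.5%.

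As a check, the ordinary chi-square was simulated on 4,500 people in 1,125 households of four. Households were allocated to the seven communities in proportion to the head counts under Sample size, true prevalence was an assumed 30% everywhere, and the correlation was placed on a latent normal scale. Rejection rates at correlation 0, 0.1, 0.2 and 0.3 were 5.5%, 11.5%, 15.5% and 23.1%. The same value on a latent scale implies a weaker correlation between the observed positive/negative results, so these rates are lower than those in the table.

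**2. Sex compared on all residents at one survey.** Sex varies within a household, so the DE formula above does not apply. The same simulation gives 4.9% to 6.2%, which is essentially nominal. Age also varies within households, so the same reasoning applies, although age was not simulated.

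**3. Cohort at one survey.** Sample size selects children individually at random within age groups. With 460 children over about 4500 / 4 = 1,125 households, a sampled child shares a household with about 460 / 1,125 = 0.41 other sampled children, so the effective m is about 1.41. Then DE = 1 + 0.41 × ICC = 1.04 to 1.12. True size is 5.5% to 6.4% on 1 df and about 6.0% to 8.2% on 6 df. Simulated single-survey sex and community contrasts reject in 4% to 6% of runs. The inflation is small, though it would be larger if eligible children live in fewer households.

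**4. Six surveys stacked as independent records (conditional).** With an assumed within-child correlation r, DE = 1 + 5r. On 1 df:

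| r | DE | True size |
|---|---|---|
| 0.1 | 1.5 | 11.0% |
| 0.2 | 2.0 | 16.6% |
| 0.3 | 2.5 | 21.5% |

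Simulation of the stacked cohort, with latent child correlation 0 to 0.3 and household correlation 0 to 0.2 (not both zero), gives 12% to 22% for sex and 25% to 63% for community.

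**The case against.** The strongest reply is that the chi-square is assigned only to cross-sectional contrasts by age, gender and community, and that most of what might be charged against it concerns analyses the protocol does not specify. Much of that stands.

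- **Before/after comparison.** A reader might infer that baseline and evaluation will be tested as two independent groups. The text names no test for that comparison, and the choice may properly sit in an analysis plan. An unpaired test there would in any case be conservative: with critical value 1.96 / √(1 − r), its true size is 2.8% at r = 0.2 and 0.6% at r = 0.5.
- **Error bars.** A reader might infer that the planned confidence intervals are wrong. The analysis section states no interval method, so there is nothing to fault.
- **Losses to follow-up.** A reader might infer that lost children will simply be left out at evaluation. No such handling is stated.
- **Stacking.** The prevalence definition counts subjects rather than tests. Read literally, each child could count once over the whole period. Stacking is one reading that the text leaves open; it is not the plan.
- **Age and sex.** At one survey these contrasts are barely affected, and single-survey contrasts within the cohort stay close to nominal.

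It is also fair to say that community differences are not the main objective, which is the effect on prevalence in children under fifteen.

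What the reply does not remove is the community comparison on whole-household data. There the protocol commits to a named test, and its own enrolment unit breaks that test's assumption. This is a stated choice, not a detail left for later.

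**Conclusion.** The concern holds for the comparison of communities on whole-population data. At one survey, a nominal 5% chi-square across seven communities has a true size of about 14% to 36% for an assumed observed-scale household correlation of 0.1 to 0.3, or about 11% to 23% if the same range is placed on a latent scale. Both ranges assume households of four and that all residents enter the comparison. Neither correlation comes from the documents.

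It holds only conditionally for repeated surveys. If the six rounds were stacked as independent records, 1-df tests would have a true size of about 11% to 22% at within-child correlation 0.1 to 0.3. The wording permits that reading but does not prescribe it.

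It does not extend to sex contrasts at one survey, to single-survey cohort contrasts, or to the baseline-to-evaluation comparison, for which no test is stated. The point is worth correcting because the affected test is one the protocol names, and the correction is cheap.

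**What to change.** - For contrasts on all residents, replace the ordinary chi-square with a household-clustered test: a Rao-Scott corrected chi-square, or a logistic GEE clustered on household.
- Name the survey that supplies the data for each age, sex and community contrast, and say whether it uses the cohort or all residents.
- Where cohort surveys are combined, or baseline is compared with evaluation, use a logistic GEE or mixed model with survey round as a factor and child as the repeated unit. A McNemar test can serve as a simple check on the two-time comparison.

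No new data are needed. Study participants already provides a household code and an individual code linked to household and community. The cost is slightly more analysis work and community p-values that will be less favourable than those from the ordinary test.

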### **Problems Anticipated**

It is anticipated that ACTs and RDTs supplies could delay. In order to avoid this, the investigators have approached the national malaria control programme to arrange for drugs and RDTs supply through the Eastern Regional Store. The investigators anticipate the number allocated to houses in the communities could be wiped and so the investigators have each house data linked to the name of the house. This could enable us to trace the participants easily. In the field the investigators will use forms that already carry the names of the families following the census. Names of new people could be added.

### **Project Management**

The PI will carry out day to day implementation and supervise of all aspect of the project. Co-PIs are part of the implementation team and will participate in the decision making at all stages of the project. The Research assistant will help in facilitating project logistics. The Regional/District Health Directorates through the health facility in Pakro will facilitate the work. The volunteers are community members that assist in data collection while the driver facilitates movements.

### **Quality Assurance**

In order to ensure the quality of data collected, 20 volunteers will be trained and 14 will be selected for the project. The questionnaires will be pretested and corrections effected. All data collected will be cross checked by two persons in the fields. To avoid loss of data, all data from the field will be recorded in the data transfer sheet before being transferred to the data management unit. All ACTs and RDTs will be

procured from the National Malaria Programme through the Eastern Region medical store. The expiry dates for all procurements made will be verified.

## **Ethical Consideration**

The ethical clearance for this study will be sought from the GHS-ERC

### *Consent Procedure*

The investigators will obtain consent at different levels. Administrative authorization will be obtained from the Ghana Health Service. There will be community consent given by the chiefs, households consent given by the head or parents/caretakers for children below 18 years, individual assent for 12-17 years old and consent for adults in each household. People from 18 years old are considered as Adults.

### *Privacy and confidentiality*

All information/samples obtained from participants and their results will be kept confidential and not be released to a third party.

### ***Data storage and Usage***

**This information will be stored in a secure location at the Epidemiology Department of NMIMR. Some staff of Epidemiology Department of NMIMR may access the data for research purposes only, such as malaria prevalence studies in asymptomatic individuals. Findings will be published with no reference to any personal identifiers. The data collected will be stored for a period of five years at NMIMR.**

### ***Data ownership***

**Data resulting from this study is own by the NMIMR.**

### *Risk*

There is no health threatening risk. Some participants may vomit within five minutes after taking the ACTs. It is assumed that if a patient vomits within five minutes he/she has not absorbed an acceptable quantity of the medicine. In this case the treatment will be repeated (Ahorlu et al., 2009). Some other patients may show adverse

reactions after taking the drugs such as stomach upset, dizziness, nausea, body weakness, etc (Sinclair et al., 2009). In order to cross check for some of these adverse events, the team will monitor volunteers for four days following treatment.

### ***Conflict of Interest***

**The PI and co-PIs declare no conflict of interest in the execution of this project.**

### ***Benefits***

All confirmed malaria parasitaemia cases will be treated for free. Continuous monitoring and treatment of confirmed cases will improve the health of residents. The study will reduce household spending on malaria thereby free some funds to be spent on other household items. This project could reduce the malaria related burden in the implementing communities.

### ***Expected Outcome/Results***

1. The effect of scaling up targeted MTTT/home-based management on hospital admissions will be understood.
2. The prevalence of asymptomatic malaria parasitaemia among afebrile children aged 6 months to 15 years and adults in the Pakro sub district will be known.
3. Reduced burden of malaria in the participating communities
4. Document challenges that hinder the scale up of mass testing, treatment and tracking of malaria in Ghana.
5. The cost benefit analysis of the scaling up MTTT intervention in the area will be known.

### ***Dissemination***

The findings of this study will be discussed at every stage with stakeholders and published.

### ***Work Plan***

Outcome	Measure	Time frame	Mile stone
Proposal development	Draft proposal is available	Aug –Oct 2016	Submitted to the STC/IRB

Ethical Clearance	Ethical clearance is obtained	Nov - Jan 2016	clearance is available
Administrative/ Ethical clearance from Ghana Health Service	Administrative and GHS-ERC clearance are obtained	Feb – April 2016	Clearance is available
Communities/durbar	Meeting/durbars held	Nov 2016	Project is accepted by the community
Mapping of households /census of participants	All households are numbered and individual identified	Nov 2016	Each households has a number
Planning for data collection	Consumables are prepared, RDTs are bought	Dec - Jan 2016	All necessary equipment and consumable are available in the field
Primary	The prevalence of asymptomatic malaria parasitaemia among afebrile children aged 6 months to 15 years and adults will be known in the Pakro sub district.	Two years  1st survey Apr - Jul 2017	Reports, Publications, Presentations at conferences and workshop demonstrating the effect of the intervention on malaria prevalence in Pakro sub district in the Eastern Region of Ghana
Secondary	Reduce the burden of malaria in the participating communities.	2nd survey Aug - Oct 2017	
	Challenges that hinder the scale up of mass testing, treatment and tracking of malaria in Ghana are documented.	3rd survey Nov - Jan 2017	
	The cost benefit analysis of the scaling up MTTT intervention in the communities will be known.	4th survey Feb - May 2018	
	Options for policy are proposed.	5th survey Jun - Sep 2018  6th survey Nov 2018 - Feb 2019	
Evaluation	What is the effect of the intervention? What is the prevalence? What are the lessons learned for scaling up.	Jan - July 2019	Report publication

## Budget & Budget Justification

### Budget

Item	specification	Cost (\$)
RDTs	Ag P.f/Pan test is a rapid, qualitative and differential test for the detection of histidine-rich protein II (HRP-II) antigen of Plasmodium falciparum in human whole blood.	19,958.4
Treatment	Artemether lumefantrin (AL) for both adults and children. The number of treated cases will be decreasing over time.	6,690
Hemocue photometer	Hb levels will be assessed to determine anaemic status.	2,582
Consumables/ materials	Gloves, tissue, zip-lock bags, safety boxes and silica gel, filter paper and PCT reagents	2,024
Incentives for Under five children	Biscuits	2,025
Data analysis	Statistician will enter the data and conduct analysis	3,000
Community entry	Meetings and durbars with chiefs	70.0
Longitudinal Cohort study	Questionnaires will be administered to parents of enrolled children or guardians	3,895.5
Training	Acquaint the volunteers with the intervention instruments and pretest.	832.32
Study of hospital admission records	To study admission trends	2,500
Communication	Communication credit enable the team liaise with the volunteers on home-based management.	1,149.12
Bags for the volunteers	These are required for transport of materials	510
Home-based management of malaria	14 community volunteers (2 from each community) conduct home-based management of malaria following the protocol.	2,112.6
Personnel	Census and mapping the study site, 6 surveys visits and the monitoring visits. The team includes 1 driver, 1 Research Assistant, 14 community volunteers and one PI.	15,232.09
Rechargeable lamp	In case there is no light (2)	123.48
Transport	Car hiring, fuel for census, surveys and monitoring	10,567
Conference / workshops and training		10,000
Publication		6,000
Total	93,508.78 + 5% contingency	98,184.209

## Explanation of Budget

### Intervention team members

The project team will be composed of one Principal Investigator (PI), 1 research assistant, and 14 community workers and a driver. We will require two cars for each survey which will last 16 days. Surveys will take place quarterly, making a total of 6 interventions over two years.

### RDTs

#### *Survey*

A pack contains 40 RDTs. Given that the target population of the targeted communities is 4,500 people, it is important to buy 5000 RDTs for each intervention (i.e. 125 packs). This is because some of the RDTs could give inconclusive results which will require that the process be repeated. Each RDT pack of 40 cost \$25.15. Each RDT cost \$0.63. The total cost for RDTs for the 6 surveys is given by  $(\$0.63 \times 5000 \times 6)$  of **\$18,900**. Pakro Health Centre is a sentinel site for monitoring malaria prevention which is being let by the Epidemiology Department of Noguchi. In this light, the RDTs and Antimalarials will be obtained from the National Malaria Control Programme, so the estimated cost which was based on RDT and drugs has been dropped.

